7.6.6. Tanner Staging

The Tanner scale (also known as the Tanner stages) is a scale of physical development in children, adolescents and adults. The scale defines physical measurements of development based on external primary and secondary sex characteristics. Subjects will be evaluated and rated as Tanner I, Tanner II, Tanner III, Tanner IV, and Tanner V. Tanner staging will occur at Visit 1 (screening), Visit 9 (Week 52) and will continue to be assessed annually for the duration of the subject's participation in the open-label phase and at the Final OL Visit.

7.6.7. Investigational Product PK

Please refer to [Section 7.7](#) for additional details regarding Pharmacokinetic Assessments.

7.6.8. Concomitant AED levels

Concomitant AED levels are not mandatory but will be collected per sites' standard of care. If AED levels are available for Visit 1 (screening), Visit 2 (baseline), Visit 3 (Week 5), Visit 4 (Week 9) and Visit 5 (Week 17), and throughout the open-label phase of the study at the timepoints noted in [Table 1](#) and [Table 2](#), the results, date and time of last AED dose and date and time of AED PK sample will be recorded in the eCRF.

7.6.9. Neurosteroid levels

A blood sample will be drawn at the screening visit to confirm the subject meets eligibility criteria and does not have plasma allopregnanolone – sulfate (Allo-S) levels ≥ 6.0 ng/ml.

Additional blood samples will be drawn at Visit 5 (Week 17) and at the Final OL Visit. The goal of this assessment is to measure levels of various neurosteroids.

Instructions for neurosteroid sample collection and processing can be found in the laboratory manual.

7.6.10. Adverse Events

Details regarding AEs and SAEs are provided in [Section 8](#).

8. ADVERSE AND SERIOUS ADVERSE EVENT ASSESSMENTS

8.1. Definition of Adverse Events, Period of Observation, Recording of Adverse Events

An AE is any untoward medical occurrence in a clinical investigation subject who has been administered a pharmaceutical product; it does not necessarily have a causal relationship with this treatment. An AE can therefore be any unfavorable and unintended sign (including an abnormal laboratory finding), symptom, or disease temporally associated with the use of a medicinal (investigational) product, whether or not related to the medicinal (investigational) product ([International Conference on Harmonisation \[ICH\] Guidance E2A March 1995](#)).

All AEs are collected from the time the informed consent is signed until the defined follow-up period. This includes events occurring during the screening phase of the study, regardless of whether or not the investigational product has been administered. All AEs reported after the initiation of investigational product will be considered treatment-emergent AEs. Where possible, a diagnosis rather than a list of symptoms should be recorded. If a diagnosis has not been made, then each symptom should be listed individually. All AEs should be captured on the appropriate AE pages in the eCRF and in source documents. In addition to untoward AEs, unexpected benefits outside the investigational product indication should also be captured on the AE eCRF page.

All AEs must be followed to closure (the subject's health has returned to baseline status or all variables have returned to normal), regardless of whether the subject is still participating in the study. Closure indicates that an outcome is reached, stabilization is achieved (the investigator does not expect any further improvement or worsening of the event), or the event is otherwise explained. When appropriate, medical tests and examinations are performed so that resolution of event(s) can be documented.

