8.1.1. Severity Categorization

The severity of AEs must be recorded during the course of the event, including the start and stop dates for each change in severity. An event that changes in severity should be captured as a new event. Worsening of pretreatment events, after initiation of the investigational product, must be recorded as new AEs (e.g., if a subject experiences mild intermittent dyspepsia prior to dosing of the investigational product, but the dyspepsia becomes severe and more frequent after the first dose of the investigational product has been administered, a new AE of severe dyspepsia [with the appropriate date of onset] is recorded on the appropriate eCRF page).

The medical assessment of severity is determined by using the following definitions:

Mild: A type of AE that is usually transient and may require only minimal treatment or therapeutic intervention. The event does not generally interfere with usual activities of daily living.

Moderate: A type of AE that is usually alleviated with specific therapeutic intervention. The event interferes with usual activities of daily living, causing discomfort, but poses no significant or permanent risk of harm to the research subject.

Severe: A type of AE that interrupts usual activities of daily living, that significantly affects clinical status, or that may require intensive therapeutic intervention.

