## 9.1 Adverse Events

Adverse events (AEs) will be coded by System Organ Class (SOC) and Preferred Term (PT) using the MedDRA®, version 16.0 or higher. The verbatim term will be included in the AE listings. Except where indicated, the summary tables will include only TEAEs. All AEs, treatment-emergent or otherwise, will be presented in subject data listings.

A treatment-emergent adverse event (TEAE) is defined as an AE that starts or worsens on or after the first dosing day of study drug. The AE analyses for the main 17-week DB treatment phase of the study will include AEs that start or worsen during that phase and will not include AEs that start or worsen during the OLE phase; ie, they will not include any AEs starting or worsening on or after the first dosing day of the OLE phase.

For the OLE phase of the study, the AEs will be summarized over just the OLE phase as well as over the entire study (combined DB and OLE phases) but the classification by the DB treatment applies only for the OLE phase summary. The summarization over the entire study will include AEs in the DB phase only from subjects who were in the GNX group during the DB phase, regardless of whether they entered the OLE, and all the subjects from the OLE phase; i.e., it will include only the AEs following GNX exposure. The summarizations over just the OLE phase will include TEAEs that start or worsen after the first day of the OLE phase; the summarizations over the entire study will include TEAEs that start or worsen on or after the first dosing day of GNX.

The TEAEs will be summarized as the number of events and the number and percentage of subjects with TEAEs. Subjects who report the same PT on multiple occasions will be counted once for the PT: under the highest severity (severe > moderate > mild) when summarized by severity and under the closest relationship (related > unrelated) to study drug when summarized by relationship. TEAEs with missing relationships will be considered as related.

If a subject reports multiple PTs for a SOC, the subject will be counted only once for that SOC. For the counting of events, all the PTs will be included in the counts, even when subjects have multiple PTs.

Pre-treatment emergent AEs by will be summarized by SOC and PT (only for the DB period summary).

TEAEs will be summarized as below.

- An overview table of TEAEs, including number of events and number (%) of subjects with
  - TEAEs

- serious TEAEs (Treatment-emergent SAEs)

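### Every change in AE severity opens a new record and SAP 9.1 has no rule to link records, so easing events can be counted as new TEAEs; benefit records on the AE page also have no stated filter

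*Protocol*

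**What the plan says.** Protocol 8.1 starts from the usual definition: "An AE is any untoward medical occurrence in a clinical investigation subject". The same section then adds that "unexpected benefits outside the investigational product indication should also be captured on the AE eCRF page", and that "All AEs reported after the initiation of investigational product will be considered treatment-emergent AEs".

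Protocol 8.1.1 requires severity to be recorded during the event, "including the start and stop dates for each change in severity", and goes on: "An event that changes in severity should be captured as a new event". Neither sentence is limited to worsening. A further sentence covers events present before dosing: "Worsening of pretreatment events, after initiation of the investigational product, must be recorded as new AEs".

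SAP 9.1 says: "A treatment-emergent adverse event (TEAE) is defined as an AE that starts or worsens on or after the first dosing day of study drug". TEAEs are reported both as numbers of events and as numbers and percentages of subjects. A subject counts once per preferred term, at the highest severity, and once per system organ class. Event counts include every occurrence. The entire-study summary combines double-blind data from the GNX arm with all open-label data, and the SAP says of it that "it will include only the AEs following GNX exposure". SAP 9.1 gives no rule for joining successive severity records of one episode and none for removing benefit records. SAP Section 11 gives the SAP precedence over the protocol where they differ.

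**The concern.** The recording rule and the counting rule do not fit together. The protocol splits one clinical episode into as many records as it has severity levels, each with a start date. The SAP then uses start dates to decide what is treatment-emergent and which phase it belongs to. An event that is getting better can therefore look like a new event on treatment.

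Safety and tolerability against placebo is a secondary objective. The TEAE tables are its main output, and they include the AEs of special interest. A rash present at screening that eases after first dose could appear as a treatment-emergent rash. In the open-label and entire-study tables, an event that arose on placebo could appear as one that followed GNX. Event counts are most exposed for AEs whose severity fluctuates. Protocol 1.2 lists somnolence, dizziness and fatigue among the commonest TEAEs with GNX, and the 4-week titration makes changes in their severity plausible.

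**Working it through.** The plan states no figure on this point, so there is nothing to reproduce. The check is to apply the rules literally to assumed records and compare the result with a rule that links records of one episode.

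Inputs: the recording rules are from Protocol 8.1 and 8.1.1, and the counting rules from SAP 9.1. The four subjects are invented for illustration.

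- A: somnolence, severe on Day 10, moderate on Day 14, mild on Day 18.
- B: rhinitis, moderate on Day -10, mild on Day 5.
- C: an unexpected benefit entered on Day 20.
- D: placebo arm, moderate cough in Week 16 that eases to mild a week after open-label start.

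| Subject and table | Literal rules: events / subjects | Linked and flagged: events / subjects |
|---|---|---|
| A, double-blind | 3 / 1 | 1 / 1 |
| B, double-blind | 1 / 1 | 0 / 0 |
| C, double-blind, only if every AE-page record is treated as an AE | 1 / 1 | 0 / 0 |
| D, double-blind | 1 / 1 | 1 / 1 |
| D, open-label | 1 / 1 | 0 / 0 |
| D, entire study | 1 / 1 | 0 / 0 |

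Double-blind total for A to C: 3 + 1 + 1 = 5 events in 3 subjects under the literal rules, against 1 event in 1 subject. Without the benefit record it is 3 + 1 = 4 events in 2 subjects, against 1 in 1.

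Three patterns follow.

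1. Change within a phase (A). Only the event count rises. Once-per-term counting at the highest severity leaves A as one subject, severe. A mild-moderate-mild episode likewise gives 1 + 1 + 1 = 3 events (2 mild, 1 moderate) but one subject, at moderate.
2. Event that began before the phase (B and D). The subject count can rise too. Once-per-term counting does not help, because the earlier record is not in that table. For D, the entire-study table would hold an event that began on placebo, contrary to its own description.
3. Benefit record (C). The outcome depends on a programming choice that the SAP does not state. If such a record were treated as a TEAE and its relationship left blank, SAP 9.1 would also class it as related.

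Scale: 100 subjects randomised 1:1 gives about 50 per arm, so one wrongly added subject is 1/50 = 2 percentage points. If 1 to 3 subjects in an arm were affected (an assumed range), the shift would be 2 to 6 points. The documents give no frequency for such records.

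**The case against.** There is a fair case that the intended meaning is clear. For events present before dosing, Protocol 8.1.1 names only worsening. The SAP also speaks of AEs that start or worsen, which suggests that easing was never meant to count. Once-per-term and highest-severity counting protects the figures most readers use. Safety results are descriptive, verbatim terms are listed, and SAP 1.2.5 already urges caution with open-label results.

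Most of this stands as evidence of intent. It does not remove the general sentence that makes any severity change a new event with its own start date, or the protocol statement that every AE reported after first dose is treatment-emergent. A programmer who follows the text gets the counts shown above. The protection at subject level is real, but it covers changes within a phase only.

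Two stronger readings are tempting, and the documents support neither.

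The first is that the SAP counts benefits as TEAEs. It counts AEs, and Protocol 8.1 defines these as untoward and mentions benefits as something additional. Miscounting is a risk from a missing filter, not a stated rule. The eCRF guidelines mentioned in Protocol 8.1.6 are not among the documents and may contain such a flag.

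The second is that benefit records would inflate GNX more than placebo, because the open-label study reported better attention, mood, behavior and sleep. Protocol 8.1 covers only unexpected benefits. Attention, sleep and a target behavior are named in a secondary objective, and the protocol collects dedicated scales for attention, mood, behavior and sleep. The earlier reports came from an uncontrolled study, through investigator narratives.

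**Conclusion.** The point holds as a gap between the recording and counting rules. Read literally, TEAE event counts are inflated whenever severity changes, and subject counts can be inflated when a pretreatment or placebo-phase AE eases after the next phase begins. A milder continuation is still adverse; the fault is that one episode is counted more than once or placed in the wrong phase. For benefits the finding is narrower: they are not AEs by definition, but nothing in the SAP keeps them out of the tables.

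The mechanism rests on the text alone and assumes that sites and programmers follow it as written. Its size cannot be derived, beyond 2 points per affected subject in an arm of about 50. The direction of any difference between arms is also unknown, since easing events can occur in both. The primary efficacy analysis does not use these records. The change is worth making because it is cheap and the affected tables serve a secondary objective.

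**What to change.** In SAP 9.1, add one derivation rule. Link the severity records of a single episode and count the chain as one event at its highest severity. Call the chain treatment-emergent in a phase only if it starts, or its severity increases, on or after the first dose of that phase. For the entire-study table, the reference is the first dose of GNX. Also state that benefit records are flagged and excluded from all AE tables.

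In Protocol 8.1.1, say that a decrease in severity continues the same event and is not a new one. In Protocol 8.1, replace the statement that all AEs reported after first dose are treatment-emergent with the SAP definition, and describe the flag for benefits.

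The cost is a few sentences, one derivation rule and modest programming. Linking needs a key or a manual review of consecutive records with the same term. The benefit flag may need a small eCRF change if none exists.

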8.1.1. Severity Categorization

The severity of AEs must be recorded during the course of the event, including the start and stop dates for each change in severity. An event that changes in severity should be captured as a new event. Worsening of pretreatment events, after initiation of the investigational product, must be recorded as new AEs (e.g., if a subject experiences mild intermittent dyspepsia prior to dosing of the investigational product, but the dyspepsia becomes severe and more frequent after the first dose of the investigational product has been administered, a new AE of severe dyspepsia [with the appropriate date of onset] is recorded on the appropriate eCRF page).

The medical assessment of severity is determined by using the following definitions:

Mild: A type of AE that is usually transient and may require only minimal treatment or therapeutic intervention. The event does not generally interfere with usual activities of daily living.

Moderate: A type of AE that is usually alleviated with specific therapeutic intervention. The event interferes with usual activities of daily living, causing discomfort, but poses no significant or permanent risk of harm to the research subject.

Severe: A type of AE that interrupts usual activities of daily living, that significantly affects clinical status, or that may require intensive therapeutic intervention.

8.1.2. Relationship Categorization

A physician/investigator must make the assessment of relationship between the investigational product and each AE. The investigator should decide whether, in their medical judgment, there is a reasonable possibility that the event may have been caused by the investigational product. If there is no valid reason for suggesting a relationship, the AE should be classified as “not related.” If a relationship between the AE and the investigational product is at least reasonably possible (i.e. the relationship cannot be ruled out) the AE should be considered "related.” The causality assessment must be documented in the source document.

The following additional guidance may be helpful:

Term	Relationship definition
Related	The temporal relationship between the event and the administration of the investigational product is compelling and/or follows a known or suspected response pattern to that product, and the event cannot be explained by the subject’s medical condition, other therapies, or accident.
Not related	The event can be readily explained by other factors, such as the subject’s underlying medical condition, concomitant therapy, or accident, and no plausible temporal or biologic relationship exists between the investigational product and the event.

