8.2.7. Regulatory Agency, Institutional Review Board, Ethics Committee, and Site Reporting

The sponsor is responsible for notifying the relevant regulatory authorities in the United States (US) and the CRO is responsible for notifying the relevant regulatory authorities in rest of world of related, unexpected SAEs.

In addition, the sponsor or the CRO is responsible for notifying active sites and central institutional review boards (IRBs) of all related, unexpected SAEs occurring during all interventional studies across the GNX program.

The investigator is responsible for notifying the local IRBs, local ethics committee (EC), or the relevant local regulatory authority of all SAEs that occur at their site as required.

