- treatment related TEAEs
- TEAEs by severity
- TEAEs leading to study drug discontinuation
- TEAEs leading to dose reduction or temporary study drug discontinuation
- TEAEs leading to death
- TEAEs by SOC and PT
- TEAE by SOC, PT, and Severity
- Study drug related TEAEs by SOC, PT
- Treatment-emergent SAEs by SOC and PT
- TEAEs leading to study drug discontinuation by SOC and PT
- TEAEs leading to dose reduction or temporary study drug discontinuation by SOC and PT
- TEAEs of special interest: rashes and the reproductive system and breast disorders system organ class
- TEAEs by PT

All AE tables will be sorted by SOC and PT in decreasing frequency of the number of subjects in the GNX group in the DB summaries and the combined groups in the OLE summaries; in case of tied frequencies, the sorting will be alphabetical.

For purposes of determining treatment emergent events, missing start and stop dates will be imputed as shown in the following table; however the actual dates, not the imputed ones, will display in the data listing.

Partial Missing Start or Stop Date	Imputed Start Date	Imputed Stop Date
Missing month, day, and year	First dose date	
Missing month and day, and the year is present	First dose date if the year is the same as the year of first dose date, else first dose date of the OLE if the year is the same as the year of the first OLE dose date, else January 1 of the AE start year.	December 31 of that year
Missing day, but year and month are present	First dose date if the year and month are the same as the year and month of first dose date, else first dose date of the OLE if the year and month are the same as the year and month of the first OLE dose date, else the 1 st of the AE start month.	Last day of that month
Missing month, but year and day are present	Assume day is also missing and impute as above	Missing month imputed as December

If an imputed start date is later than the stop date, then the stop date (after any needed imputations) will be used instead for the imputed start date.

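### Protocol 8.1.2 defines a related AE more narrowly in its table than in its text, so a plausible event with another possible cause fits neither table row

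*Protocol*

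**What the plan says.** Protocol 8.1.2 asks the physician or investigator to judge whether the product may have caused each AE, with two possible outcomes. The running text sets both thresholds. For the lower one: "If there is no valid reason for suggesting a relationship, the AE should be classified as" not related. For the upper one, where a relationship is "at least reasonably possible (i.e. the relationship cannot be ruled out) the AE should be considered" related. Neither sentence makes the answer depend on whether something else could explain the event.

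A table follows, introduced as additional guidance, with a column headed as the relationship definition. Its *Related* row opens with: "The temporal relationship between the event and the administration of the investigational product is compelling and/or follows a known or suspected response pattern". The row then runs on from that pattern to a second condition, joined by 'and': "known or suspected response pattern to that product, and the event cannot be explained by the subject’s medical condition, other therapies, or accident". The *Not related* row also has two joined parts: other factors must readily explain the event, and "no plausible temporal or biologic relationship exists between the investigational product and the event".

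The classification is used in three places:

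- Protocol 8.2.7 makes the sponsor or CRO responsible for "notifying active sites and central institutional review boards (IRBs) of all related, unexpected SAEs", and applies the same test to notification of regulatory authorities.
- Protocol 8.2.4 makes an SAE discovered after study completion reportable when it is considered related.
- SAP 9.1 lists "Study drug related TEAEs by SOC, PT" among its tables, ranks relationship on two levels, and counts a missing relationship as related.

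The SAP does not define relatedness. The rule in SAP Section 11 that the SAP prevails over the protocol therefore settles nothing here.

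**The concern.** The text asks whether the product can be excluded as a cause. The table's *Related* row asks whether everything else can be excluded. These are different questions, and in this population the answers will often differ. Subjects have CDD with seizures uncontrolled on at least two medicines and may take 0 to 4 background AEDs (Protocol 4.1), so the disease or another medicine will often be an available explanation.

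If some of the up to 50 sites (Protocol 3.3) follow the text and others follow the *Related* row, the same event can receive different labels. The pooled related-TEAE counts would then rest on no single definition. Whether an unexpected SAE counts as related for expedited notification could also depend on which half of the section the investigator used.

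**Working it through.** The plan gives no figure on this point and no arithmetic applies. The check is to set the two definitions side by side. For any AE, let:

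- **P** = a relationship is plausible, that is, it cannot be ruled out. This treats the text's reasonable possibility and the table's plausible relationship as the same thing.
- **C** = timing is compelling and/or the response pattern is known or suspected. C implies P.
- **E** = the medical condition, another therapy or an accident can explain the event.

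Text: related = P; not related = not P.
Table: *Related* = C and not E; *Not related* = E (readily) and not P.

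| Case | Text | Table |
|---|---|---|
| C, P, not E | related | *Related* |
| C, P, E | related | neither row |
| not C, P, not E | related | neither row |
| not C, P, E | related | neither row |
| not P, E (readily) | not related | *Not related* |
| not P, not E | not related | neither row |

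Two things follow. First, the table classifies only two of the six cases. The text classifies all six. Second, wherever the table does give a label, it is the same label as the text. The inconsistency is a gap created by the extra condition in the *Related* row. It is not a swap of labels.

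A worked case from the protocol's own content is seizure worsening after abrupt discontinuation of the product:

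- Protocol 8.1.4 requires significant worsening of disease symptoms to be recorded as an AE.
- Protocol 4.5.1 warns that abrupt discontinuation may bring an increase in seizure number or severity, so P holds and C may hold.
- CDD can itself explain worse seizures, so E holds.
- Under the text the event is related. It fails *Related* in the table because the medical condition can explain it. It fails *Not related* because a plausible relationship exists.

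Protocol 8.2.3 names convulsions among its examples of important medical events that may be SAEs, so such a case can be serious. Whether it would also be unexpected depends on the Investigator's Brochure (Protocol 8.2.1), which is not part of these documents.

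Uses that depend on the label:

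- the related-TEAE summaries (SAP 9.1);
- notification of related, unexpected SAEs (Protocol 8.2.7);
- SAEs discovered after the study (Protocol 8.2.4).

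Uses that do not:

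- reporting of all in-study SAEs to the sponsor within 24 hours, whatever the relationship (Protocol 8.2.2, 8.2.4);
- the investigator's own notification of all SAEs to the local IRB, EC or authority as required (Protocol 8.2.7);
- DMC access to unblinded safety data (Protocol 9.4);
- the SAP 9.1 tables of all TEAEs, serious TEAEs, discontinuations and events of special interest.

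**The case against.** The strongest reply is that the text carries the instruction while the table is only offered as help, so a careful investigator would let the text govern and fill the gap with *related*. That is a natural reading and it limits the damage. It does not remove the problem. The protocol never states it, and the table's column is headed as a definition and adds a condition that the text lacks.

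A second reply is that the SAP counts a missing relationship as related, so an event left blank because neither row fits is handled conservatively. This is true for blanks only. It does nothing for an event that a site enters as not related.

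Three stronger readings are tempting, and the documents do not support them.

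- *The table lets a site call a possibly drug-caused SAE not related.* As written it does not, because the *Not related* row excludes any event with a plausible relationship. Such a label would require a site to treat failure of the *Related* row as sufficient for *Not related*. Two mutually unfitting rows invite that misreading, but they do not instruct it.
- *Somnolence shows the size.* Applying the 33.9% seen on GNX in the fragile X trial (Protocol 1.2) to 50 subjects gives 0.339 × 50 ≈ 17, and a reader might infer that up to 17 related events are at stake. That rate comes from another disease at up to 36 mg/kg/day, against up to 63 mg/kg/day here. Protocol 2.1 reports no somnolence to date among the CDKL5 subjects in Study 1042-0900, although only 7 were enrolled. Somnolence is also among the most frequent TEAEs and was anticipated from the mechanism (Protocol 1.2), so it is a poor example for a notification route limited to unexpected SAEs.
- *Safety signals would be lost.* In-study SAEs reach the sponsor regardless of label, and the randomized comparison of all TEAEs does not use it.

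**Conclusion.** The point holds as an internal inconsistency in Protocol 8.1.2. The text makes every plausible event related. The table's *Related* row also requires that no other explanation exists, and its *Not related* row requires that no plausible relationship exists. A plausible event with an alternative explanation therefore has no place in the table, and the protocol does not say which wording governs.

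The consequence is confined to outputs that use the label: the related-TEAE summaries, notification of related, unexpected SAEs, and reporting of SAEs found after the study. For the last two, Protocol Section 8 describes no separate sponsor causality assessment that would correct a site's label. The number of events affected cannot be estimated from the documents, because it depends on how sites read the section and on medical judgment case by case.

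The conclusion rests on reading the text's reasonable possibility and the table's plausible relationship as equivalent, and on the table's conditions being joined by 'and', as they are printed.

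**What to change.** Either delete the table, or reword it so that the two rows cover every event once:

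- *Related*: there is a reasonable possibility of a relationship that cannot be ruled out, even if the condition, other therapies or an accident could also explain the event.
- *Not related*: there is no reasonable possibility of a relationship.

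Add one sentence stating that the text governs, and tell sites by memo. A re-query limited to SAEs already marked not related is not needed. It would reclassify in one direction only.

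The cost is a wording change and a site memo. The downside is that somewhat more events will be classed as related, with possibly a few more expedited reports, which the existing text already calls for. No endpoint, sample size or efficacy analysis changes.
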